Data collection will occur outside hookah cafés in the Atlanta, GA metro area. Atlanta was chosen as the study site because Georgia's weak smoke-free air law allows smoking in bars and restaurants, including hookah cafés. There are over 100 hookah cafés in the Atlanta metropolitan area and Atlanta is home to 57 colleges and universities. The number of cafés and young adults, and the weak smoke-free air laws make Atlanta the ideal location for this study. We will partner with one pilot café and up to 31 additional cafés to allow study activities, including collecting data with customers before café entry and after café exit, and display of study-produced health warnings about hookah smoking during the times when data collection is occurring. Participants will complete data collection outside of the café at two time points, before entry into the café and after exit from the café.

Subject Selection Criteria

Participants will be those planning to enter a hookah café where the study is being conducted. We aim to have 15 participants complete Time 1 (before café entry) and Time 2 (after café exit) data collection at each café for each arm. In order to account for attrition between time points, we will enroll up to 30 participants at each café during each data collection period. We will schedule data collection periods for when the café is most busy, based on information provided by the café manager or owner.

Inclusion Criteria

- Planning to enter the hookah café where study is being conducted
- Age 18 or older
- English speakers
- Planning to smoke hookah inside
- Planning not to smoke cigarettes, cigars, cigarillos, or marijuana while at the hookah café
- Had not previously entered the café earlier in the day on the same day/night as data collection
- Has not been approached to participate in the study at another café or another day/night at the current café
- Are not employees of the business
- Have capacity to participate as determined by the staff member conducting eligibility screening

Exclusion Criteria

- Not planning to enter the hookah café where the study is being conducted
- Age 17 or under
- Non-English speakers
- Not planning to smoke hookah in the café
- Planning to smoke cigarettes, cigars, or marijuana while at the hookah café
- Are employees of the business
- Has not been approached to participate in the study previously
- Had previously entered the café on the same day/night as data collection

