- Does not have capacity to participate as determined by the staff member conducting eligibility screening

Sample Size

- We will enroll up to 1,560 participants in total, across the 32 cafés (this includes up to 30 participants per night, per café. The goal is 15 **completions** per night, per café).

Interventions and Interactions

Intervention Arm

Study staff will place signs containing a text-only warning (selected from a pool of four warnings on lung damage, heart damage, carbon monoxide poisoning, and stunting fetal growth tested in WT Warnings Aim 2 – IRB00091946) in various locations around the café, as agreed upon with the café owner or designated representative. Locations may include the hookah pipes, tables, interior wall signs, countertop signs, menus,

and bathroom signs (see Figure 1. Table Sign). Sign placement and quantity may differ between cafés. Signs will be removed by study staff at the end of each data collection period.

Control – No Warnings

In the Control arm, there will be no signs placed by the study team at any location within the café.

Data Collection

The timing of data collection periods will be agreed upon in advance between the study team and the café owner, manager, or their designee. When the data collectors first arrive at the café, they will introduce themselves to the café point person and place signs in the agreed-upon locations and will document the locations in the café record (on intervention nights). Additionally, photographs of sign placement will be taken.

The study team will set up tables outside the café, where data collection will be completed. In 2017, we completed a pilot study to test these methods (IRB00044196), which worked well. Data collection will be conducted during café hours, when young adults are most likely to visit waterpipe cafés, based on the advice from café employees. Data collectors will approach individuals before they enter the café to determine interest in the study. Interested individuals may also approach the data collectors. Data collectors will conduct eligibility screening with interested individuals (described above).

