Data collectors will also make a determination, based on their interaction with the participant, of the participant's capacity to participate in the study. If they determine that the person does not have capacity, they will mark this on the Eligibility Form and the participant will be Not Eligible. If they determine that the person does have capacity, they will mark the participant such on the Eligibility Form and will continue with the Consent process. Determination of capacity to participate will be based on whether people can adequately answer the eligibility screening questions. Eligible participants will be read the consent information by a data collector prior to enrollment and provide verbal consent. A printed consent document will be available for participants if they ask to see it.

After completing the consent process, participants will be given a wristband with their participant ID. Then, they will complete a brief survey about their hookah use behaviors, demographics, and recent use of other combustible products. They will enter their email into a Qualtrics link managed by Ewald & Wasserman to receive their first (\$25) electronic gift card; this is not stored with study data, although it is linked to PID. Next, participants will provide up to two samples of expired carbon monoxide (eCO) by blowing into a carbon monoxide (CO) monitor. This non-invasive process involves taking a deep breath, holding it for 15 seconds, and then exhaling into a sterile tube until the lungs are completely empty. Expired CO is a well-established measure of tobacco smoke exposure. Participants will then be able to enter the café as planned. All participants will be asked to return to the data collectors after exiting the café to complete the follow-up measures. If the data collection period is scheduled to end before the café closes, data collectors will instruct the participants to come outside for Time 2 measures before the data collection period will end. Upon exiting the café, participants will complete a similar brief survey, provide their email again for their second (\$50) compensation, and provide up to two new samples of eCO, using the same procedure as described above. Participants will be debriefed on the purpose of the study and the CO measure. The debrief form will also have resources for more information about CO and health harms of hookah smoking, and contact information for the study PI, the Wake Forest IRB, and E&W for assistance with compensation.

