The participant incentives are not intended to be an enticement to smoke hookah within the café, but rather as compensation for time needed to complete the surveys and eCO monitoring, which we anticipate will take up to 20 minutes at each time point. Participants will only be eligible if they indicate they are planning to smoke hookah in the café. We will not recruit people to come to the café, but rather recruit café customers to participants in the study. Participants will be instructed to behave as they normally would in the café. The incentive will not be able to be used in the café.

Figure 1. Table Sign

Pilot/Soft Launch

We will conduct a pilot/soft launch with a single hookah café to assess feasibility of the protocol and to make changes, if required, before conducting the full trial. Any changes to protocol and/or measures will be submitted as amendments before conducting the remainder of the trial. If no changes are made as a result of the soft launch, this café will be included in the final study sample. If significant changes are made as a result of the soft launch, we will conduct the study with up to 25 additional cafés and the data from the soft launch café will not be included in the final dataset. We will implement both text-only and pictorial warnings on different nights at the pilot café to fully test the two versions of the intervention signs, in addition to the control arm.

Outcome Measure(s)

Primary Outcome

Change in Expired Carbon Monoxide from baseline to follow-up. We will use eCO, an objective, biological marker of waterpipe tobacco consumption. There is a linear relationship between waterpipe tobacco smoking intensity and carboxyhemoglobin concentration, and eCO is strongly correlated with several topography measures of waterpipe smoking. Carbon monoxide has a half-life of 3-4 hours and is influenced by other forms of combustible tobacco; therefore, the primary outcome will be the change in eCO from before entry to after café exit, known as eCO boost. We will also record the percentage of carboxyhemoglobin concentration measured by the CO monitor.

Secondary Outcome(s)

None

Other Outcomes

Behavioral intentions. Participants will be asked at Time 2 three items assessing their expected hookah smoking within the next month. Items will be averaged to create a composite score of intent to continue the behavior within the next month.

1. How interested are you in smoking tobacco in a hookah in the next month?

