Warning recognition (Intervention Arms Only). Participants will be asked to select the warning(s) that they saw at the café from a selection of the four possible warnings for their study arm. For each warning message that they report having seen, they will be asked to select where they saw the warning from a list of possible locations.

Social interactions. For each warning selected in the Warning Recognition section, participants will be asked if they discussed the warning with others. If they answer positively, they will be given a list of topics to choose from to describe what they talked about, including a free-text option.

Perceived influence of warning on smoking behavior. Participants will be asked whether they changed their smoking behavior as a result of the warning(s) they saw (as reported in the Warning Recognition section). They will be asked to report whether they smoked more, less, or the same amount as they usually do. These items will be asked for each warning the participant reports seeing.

Time spent in the café. Duration of time in café will be calculated from the time of completion of eCO measurement at Time 1 to start of survey at Time 2. Additionally, we will utilize a subjective measure of time spent in the café: Compared to what you planned, how long did you stay at the café/lounge/bar? (Longer, shorter, about the same).

Analytical Plan

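### The derived time in café starts and stops outside the café, so any wait before entry or after exit is counted as time inside

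*Combined protocol and SAP*

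**What the plan says.** In Other Outcomes, the entry on time spent in the café gives this rule: "Duration of time in café will be calculated from the time of completion of eCO measurement at Time 1 to start of survey at Time" (that is, the follow-up contact). The same entry adds a self-report item with three categories: longer, shorter or about the same as planned.

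The Setting section places both contacts outside: "Participants will complete data collection outside of the café at two time points, before entry into the café and after exit from the café". The Data Collection section agrees: "The study team will set up tables outside the café, where data collection will be completed". It also gives the order of steps. At Time 1 the breath test comes last, after which "Participants will then be able to enter the café as planned". At Time 2 the survey comes first: "Upon exiting the café, participants will complete a similar brief survey", followed by the email entry and the breath test.

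On workload, each contact is one that "we anticipate will take up to 20 minutes at each time point". Subject Selection Criteria allows up to 30 enrolled per café per data collection period, with 15 completers as the aim. The number of tables, tablets or staff is not stated.

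**The concern.** The outcome is named as time in the café, but neither clock point is café entry or café exit. A person who finishes Time 1 and then waits outside for companions is already on the clock. A person who comes out and waits for a free tablet or data collector is still on it.

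This is the plan's only measure of stay in minutes, and so its only objective evidence on whether a warning shortened the visit. Waiting that has nothing to do with smoking behaviour is mixed into it. If the true entry and exit times are not recorded on the night, they cannot be recovered later.

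**Working it through.** The plan gives no expected duration, standard deviation or power for this outcome, so there is no stated figure to reproduce. The check is to line up the time stamps and then see how large the error could be.

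**1. What the interval contains.** Write the recorded duration as

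recorded = (entry − end of Time 1 eCO) + (exit − entry) + (start of Time 2 survey − exit).

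The middle term is the quantity wanted. The first and third are time outside. Neither is recorded under the procedures described, so neither can be subtracted.

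**2. Is waiting plausible?** At the stated ceilings, 30 Time 1 contacts and 15 Time 2 contacts take 30 × 20 + 15 × 20 = 900 minutes, or 15 station-hours per period. The Analytical Plan expects people to smoke in company, since it adjusts for the number of companions. Data Collection also has participants called out for Time 2 when the period ends before closing, which would bunch returns.

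**3. Hand example (assumed: four companions, two stations, 20 minutes per contact, 90 minutes inside, party enters and leaves together).** A and B finish Time 1 at minute 20, C and D at minute 40. All enter at 40 and leave at 40 + 90 = 130. Two Time 2 surveys start at 130 and two at 150.
- Same order at both ends: A and B record 130 − 20 = 110; C and D record 150 − 40 = 110.
- Reversed order: A and B record 150 − 20 = 130; C and D record 130 − 40 = 90.

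The true stay is 90 for all four, so the error is not a constant that always cancels between people.

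**4. Both ends together, simulated.** Assumed: 20 people who all return, parties of 1, 2 or 4 arriving over 150 minutes, contacts of 10–20 minutes, true stay Normal(90, 20), companions entering and leaving together, stations shared between Time 1 and Time 2. Mean overstatement with no arm difference in contact length:
- 6 stations: 0.1 to 5.5 minutes
- 4 stations: 1.3 to 8.7 minutes (1% to 10% of 90)
- 3 stations: about 5 to 20 minutes

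**5. Does it differ by arm?** The warning recognition entry is for the intervention arm only, and it asks for the place as well: "For each warning message that they report having seen, they will be asked to select where they saw the warning from a list of possible" (places in the café). Items on discussion and perceived influence follow. All of these come after the Time 2 survey has started, so they add 0 minutes to that participant's own duration. They could matter only by slowing turnover for people who return later.

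A first-come-first-served queue at Time 2 shows the range. Assumed: returns spread over 180 minutes, singly or in threes; base contact 10 or 20 minutes; intervention contact 1 or 3 minutes longer.

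| Returners | Stations | Mean wait, control (min) | Extra mean wait, intervention (min) |
|---|---|---|---|
| 15 | 6 | 0.0–0.4 | 0.0–0.2 |
| 15 | 4 | 0.0–3.3 | 0.0–1.1 |
| 15 | 2 | 0.8–20.2 | 0.3–7.0 |
| 30 | 6 | 0.0–2.5 | 0.0–1.3 |
| 30 | 4 | 0.2–11.8 | 0.1–5.1 |
| 30 | 2 | 5.5–69.5 | 2.6–20.7 |

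The result runs from nothing to a material difference, and the inputs that decide it are not in the protocol.

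**The case against.** The strongest reply is that nothing in the protocol mentions a queue. Surveys are self-administered on tablets, so a returner may be able to start before the previous person has finished the email and breath-test steps. The simulations hold a station for the whole contact, and the hand example takes two stations with every contact at the 20-minute ceiling. With enough tablets the error is close to nil. That stands, and it is why the size is given only as a range.

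It is also fair that waiting of equal length in both arms adds noise but does not bias the contrast, that this is one of many other outcomes, and that the self-report item does not use these stamps. That item, however, gives no minutes and cannot correct the derived duration.

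The data forms are listed in the Appendix but not reproduced, so a time field may already exist. The stated derivation would still not use it.

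A reader might infer more: that the intervention arm waits longer, so the rule hides a true shortening under warnings. The protocol does not support this. The extra items follow the participant's own end stamp; the location, discussion and influence items are asked only about warnings reported as seen; and one contact length is given for both arms. Every café also starts in control, so order, staff experience or turnout could move waits either way. An indirect effect through slower turnover is possible, but neither its presence nor its net direction is shown.

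**Conclusion.** The concern holds as a point about measurement. The rule counts unmeasured time outside at both ends, which overstates some stays and adds variation between people whose stays were the same. That conclusion rests on the protocol's own order of steps and needs no assumption. The size does: from about nil to many minutes per person, depending on station numbers, contact times and party size. A difference between arms is neither established nor excluded.

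Severity is low. The primary eCO boost does not use this interval. The reason to act is that the correction is cheap and the missing times cannot be reconstructed afterwards.

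**What to change.** Have the staff already at the tables log the clock time against the wristband ID twice: when the participant goes in after Time 1, and when the participant comes back to the table, before any wait for a tablet or data collector. Two fields on the eCO form or café record are enough. If the forms already hold such fields, only the definition changes.

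Replace the derivation sentence with one that defines duration as logged café entry to logged return at Time 2. Keep the present interval only where a log time is missing, flag those records, and report their number by arm.

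The cost is a few seconds of staff time per participant and some missed log times, most likely when the tables are busy, which is why the flag matters. Logged return still includes the walk from the door to the table, which should be short.

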The sample size will allow us to detect meaningful differences in the eCO boost between study arms. We estimate the minimum difference in eCO boost detectable between the two arms (intervention vs control) with 80% power between two periods I using a cluster randomized crossover trial design with a minimum of 20 cafés, each with completed data for 30 café patrons (15 per arm). Sample size is based on formulae from Giraudeau et al. (2018) that takes into account both the intraclass correlation coefficient r (correlation within a café) and the inter-period correlation h induced by the crossover design.¹³ We consider both small and moderate ICCs or $r=0.10$ and $r=0.30$ and a smaller h specified to be half of r as recommended by Donner et al. (2004).¹⁴ A review of the literature¹⁵⁻¹⁸ suggests a standard deviation of $s=30$ parts per million (ppm) for the change in eCO. Based on these assumptions, we will have 80% power to detect differences in eCO boost between two periods of 8.81ppm for a low r and 11.78ppm for a moderate r . In one of the few studies in waterpipe cafés, the mean absolute change in CO was 51.7ppm with a relative boost of 795%.¹⁵ we are more than sufficiently powered to detect differences this large as well as much smaller changes in the range of 8.81ppm to 11.78ppm. We can convert this to number of fewer puffs based on data that a single puff results in a 0.4ppm eCO boost.¹⁹ We will be able to detect a reduction of between 22.0 and 29.4 puffs.²⁰ This is consistent with the reduction in mean puffs (26.0) found in the lab-based pilot study of WTS warnings.²¹

A hierarchical linear modeling (HLM) approach (model C1 in Turner et al. 2007) will be used for the analysis.¹³⁸ In contrast to cluster-level methods, which aggregate data, hierarchical modeling offers more flexibility and allows us to incorporate both café-level and individual-level covariates, as well as the correlation

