of individuals within study arm within cafés. We let eCO_{ijk} represent the outcome measurement for individual k within study arm j within cluster (café) I , assumed continuous and normally distributed. The model will include a fixed effect for study arm (intervention or control) and random cluster and cluster-arm effects. Models will adjust for individual-level sociodemographics and tobacco use at baseline. In secondary analyses, we will examine the impact of sociability of waterpipe behavior by adjusting models for the number of people with whom the individual is smoking in the café. Secondary analyses will examine the impact of text versus pictorial warnings. These hierarchical models will be fit using PROC MIXED in SAS. Because the intervention effect is estimated within clusters, it is also adequate to model fixed cluster effects but retain random cluster-arm effects. Turner (2007) demonstrated through simulation that these two models perform similarly with 18 clusters with slight differences depending on the degree of correlation. We will examine both approaches as a sensitivity analysis.²² Using the same HLM modeling approach, we will perform analyses on secondary outcomes shown in Table 5.

Human Subjects Protection

Overview

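### If companions are co-enrolled and smoke alike, the standard error for companion count in the secondary sociability analysis is too small, because the model has no party term

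*Combined protocol and SAP*

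**What the plan says.** The Analytical Plan of the combined protocol and SAP gives the model for eCO boost: "The model will include a fixed effect for study arm (intervention or control) and random cluster and cluster-arm effects". It also adjusts for individual sociodemographics and baseline tobacco use. A secondary analysis examines sociability by "adjusting models for the number of people with whom the individual is smoking in the café". No party or table effect and no party-robust variance is mentioned.

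Recruitment is by individual. Under Data Collection, staff approach people before they enter the café. The inclusion and exclusion lists contain no limit of one person per party. Subject Selection Criteria allows up to 30 enrolled at each café in each data collection period, to obtain 15 completers.

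The sample-size paragraph rests on "the intraclass correlation coefficient r (correlation within a café) and the inter-period correlation h induced by the crossover design". It takes r as 0.10 or 0.30, with "a smaller h specified to be half of r". It does not say whether r covers people who smoke together.

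**The concern.** The plan treats hookah smoking as social: it wants to know whether company matters, and it asks participants whether they discussed the warning with others. People who arrive together plausibly stay for a similar time and may share a pipe (both are assumptions). Their boosts would then be more alike than those of two strangers in the same café on the same night.

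Given the café and café-arm effects, the planned model makes two friends no more alike than two strangers. Companion count takes nearly the same value for everyone in a party and varies between parties within a café-arm. It is therefore tested against individual-level residual variance, and one party counts as several independent observations. The café-arm effect cannot correct this, because the covariate varies below that level. At stake is a chance association between company and smoke exposure being reported with more confidence than the data support.

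**Working it through.** **Inputs from the Analytical Plan.** 20 cafés, 15 completers per café-arm, SD 30 ppm, r = 0.10 or 0.30, h = r/2, 80% power. Two-sided 5% is assumed, since alpha is not stated.

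**Inputs not in the documents (assumed).** Party sizes 1–4 or 1–6, each size equally frequent and all members enrolled; extra within-party correlation ρ of 0 to 0.3, as a share of total variance.

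**Step 1: the plan's own figures.** Detectable difference = 2.8016 × √{(2 × 30²/(20 × 15)) × [1 + 14r − 15h]}.

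- r = 0.10: 2.8016 × √(6 × 1.65) = 8.81 ppm (stated 8.81).
- r = 0.30: 2.8016 × √(6 × 2.95) = 11.79 ppm (stated 11.78).

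The figures reproduce. In this formula r is the average correlation over all pairs in a café-arm. If r already includes companions, nothing changes.

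**Step 2: companion-count coefficient, approximate formula.** Within a café-arm the remaining variance is 1 − r = 0.9 (r = 0.10), so the correlation between companions given the café-arm is ρ/0.9. For a party-level covariate x, with people in parties of size g, the true variance exceeds the model's by the factor

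1 + C × ρ/0.9, where C = Σ w(x − x̄)²(g − 1) / Σ w(x − x̄)² and w is the share of people in parties of size g.

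- Sizes 1–4: w = 0.1, 0.2, 0.3, 0.4 and mean size 3. C = (0.2 × 1 + 0 × 2 + 0.4 × 3)/1.0 = 1.4.
- Sizes 1–6: w = g/21 and mean size 4.33. C = 5.48/2.22 = 2.47.

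Model SE / true SE = 1/√(1 + Cρ/0.9), and the false-positive rate is 2 × [1 − Φ(1.96 × ratio)].

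| Party sizes | ρ | SE ratio | False-positive rate |
|---|---|---|---|
| either | 0 | 1.00 | 5.0% |
| 1–4 | 0.1 | 0.93 | 6.8% |
| 1–4 | 0.3 | 0.83 | 10.6% |
| 1–6 | 0.1 | 0.89 | 8.2% |
| 1–6 | 0.2 | 0.80 | 11.5% |
| 1–6 | 0.3 | 0.74 | 14.7% |

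**Step 3: simulation of the planned model (REML, true coefficient zero, 20 cafés × 2 arms × 15, r = 0.10, h = 0.05).**

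- Sizes 1–6, 1,000 trials per setting, ρ = 0, 0.1, 0.2, 0.3: SE ratios 1.05, 0.90, 0.80, 0.74; false-positive rates 4.5%, 8.6%, 11.3%, 14.9%. The Monte Carlo error at 8.6% is √(0.086 × 0.914/1000) = 0.9 points.
- Sizes 1–4, 480 runs, ρ = 0.3: mean SE 1.23 under the plan against 1.49 with a party effect (ratio 0.83); false-positive rate 9.8% against 5.9%.
- A further run at ρ = 0.3: planned-model SE 1.19 against a true SD of 1.53 (ratio 0.78); about 13% false positives, about 7% with a party effect.

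The formula and the simulations agree.

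**Step 4: the arm effect.** In the 1,000-trial simulations, the arm effect had an SE ratio of 0.97 to 1.03 and a false-positive rate of 4 to 6% for ρ up to 0.5, with or without companion count in the model. The café-arm effect absorbs the party variance for that comparison.

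**The case against.** The strongest reply is that the only primary outcome is eCO boost compared by arm, that the secondary outcomes section lists none, and that the arm test keeps its size. This is right, and the point does not reach the primary analysis. A reader might infer that ignoring parties makes the warning effect look more precise than it is. Step 4 does not support that.

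A second reply is that adjusting for companion count may be meant only to yield an adjusted arm effect, which has sound error bars. That reading is open. However, the stated purpose is to examine the impact of sociability, and a reader would naturally look to the companion-count coefficient for that.

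A third concerns power. A reader might infer that 80% power at 8.81 and 11.78 ppm is not delivered. That would follow only if r left companions out. With two co-enrolled companions per person, the bracket in Step 1 would gain 2ρ. At ρ = 0.1 and 0.3 this gives 9.33 and 10.29 ppm for r = 0.10, and 12.18 and 12.93 ppm for r = 0.30. But r is described as correlation within a café, which can be read as covering all pairs, and nothing excludes companions. The first two figures also lie inside the plan's own range. No error in the power statement is shown.

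Finally, party size, co-enrolment and ρ are all assumed, and loss of companions between time points would shrink the effect. This stands, and it is why the size is given as a conditional range. Nor can it be said that no party identifier exists: the eligibility form and surveys are listed in the Appendix but not shown. An identifier there would still be unused by the model as written.

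**Conclusion.** The point holds in a limited, conditional form. With café and café-arm as the only random effects, the companion-count coefficient has too small a standard error if companions are co-enrolled and have eCO boosts more alike than strangers on the same night. For assumed extra correlation of 0.1 to 0.3, the understatement is roughly 10 to 25% (7% in the mildest case worked), with a false-positive rate of about 7 to 15% at a nominal 5%. It disappears if that correlation is zero or one person per party is enrolled. The consequence is confined to a stated secondary analysis. The primary result, the arm effect adjusted for companion count, and the stated detectable differences all stand.

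**What to change.** At Time 1, record a shared party number for people who arrive together, next to the participant ID, unless the eligibility form or surveys already do so. This is best done on the night, since who came with whom may not be recoverable later. In the sociability analysis, add a random party effect nested in café-arm (one further RANDOM term in PROC MIXED), or use party-robust standard errors. If data collection is over and no identifier exists, report the companion-count result with a caveat that its interval may be too narrow.

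The cost is one data field and a somewhat wider interval for that coefficient. A sentence in the sample-size paragraph saying that r includes companions would be a useful clarification, but it is optional and corrects no error.
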